SUBJECTS, MATERIALS AND METHODS

The current study aims to investigate whether incorporating mini squat exercises at different knee flexion angles into a leg press training program enhances hamstring- quadriceps ratio H:Q ratio in football players.

Design of the study:

This study will follow a randomized controlled trial (RCT) design.

Study setting

The study will be conducted at the outpatient physical therapy clinic of Jazan University Hospital, kingdom of Saudi Arbia.

Sample size:

The sample size for this study was determined using G*Power version 3.1.9 (Heinrich-Heine-University, Düsseldorf, Germany). An a priori power analysis was conducted for a repeated measures MANOVA with between-subject factors, setting the alpha level (α) at 0.05, desired power ($1 - \beta$) at 0.80, Pillai's trace (V) at 0.1989, and effect size $f^2(V)$ at 0.2877, targeting isometric muscle strength across four independent groups. The analysis indicated a minimum required sample size of 48 participants, allocating 12 per group. To compensate for possible dropouts, the total sample was increased to 60 participants, with 15 individuals per group (**Wirth et al., 2016**) (figure 3).

[figure not shown]

Fig 3:sample size calculation using G power

Randomization, allocation concealment, and blinding

The enrolled participants will be randomized in a simple randomization way using (www.randomizer.org/links/) by another participant not involved in the data collection. Allocation concealment will be ascertained using sealed, opaque, sequentially numbered envelopes. The participants will be blinded to the assigned intervention group.

Participants

Sixty male football players from Al-Ahli and Al-Ittihad football clubs in the Kingdom of Saudi Arabia. Participants will be asked to sign a written informed consent that includes participation in the experimental trial, permission to use data and/or pictures, and informing them of their right to withdraw at any time (**Appendix I**).

Participants will be randomized into 4 equal groups: an experimental group (A, B, and C), and a Control group (D).

Experimental groups (A, B, and C)

Group A: Fifteen participants will receive mini-squat exercises at 30° knee flexion and leg press exercises

Group B: Fifteen participants will receive mini-squat exercises at 45° knee flexion and leg press exercises

Group C: Fifteen participants will receive mini-squat exercises at 60° and leg press exercises

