Control group D: Fifteen participants will receive leg press exercise program only.

Inclusion criteria:

Participants having the following criteria will be included in the study:

1. Male football players aged between 18–30 years (**Scoz et al., 2021**).
2. Body Mass Index (BMI) between 18.5 and 24.9 kg/m² (**Walsh et al., 2018 & Sattar& Lean, 2009**).
3. Currently training or playing with a registered football club/team.
4. Hamstring-to-Quadriceps (HQ) strength ratio of ≥ 0.6 (**Çelebi et al., 2018**).
5. Having no oral or injectable non-steroidal anti-inflammatory drugs (NSAID), 2 weeks before starting study.
6. Having no oral injectable corticosteroids 3 months before starting the study.

Exclusion criteria:

Participants having any of the following criteria will be excluded from the study:

1. History of acute or chronic injury to the knee, hip, or ankle joint
2. Undergoing any other rehabilitation or physical therapy programs during the six weeks before starting the study
3. Diagnosed with neurological or systemic disorders affecting muscle function or balance

4. Participation in competitive sports or high-intensity training outside the study protocol during the study period
5. Presence of any contraindication to exercise, such as uncontrolled hypertension or heart conditions.
6. Clinically free from lower limb injuries.
7. Having no history of neurological, cardiovascular, or musculoskeletal disorders.

Instrumentation:

a. Isokinetic dynamometry:

Isokinetic dynamometry (**BiodeX System 4 Pro**) is considered the gold standard for assessing muscle strength and HQ ratios, offering valid and reliable measurements through controlled torque assessment during concentric and eccentric contractions. Its criterion validity is well established, and reliability is consistently high, with ICCs ranging from 0.85 to 0.99. Furthermore, its ability to calculate both conventional and functional H:Q ratios provide a reproducible measure of knee muscle balance, making it highly valuable for evaluating injury risk, rehabilitation outcomes, and return-to-sport readiness (**Ayala et al., 2012**) (figure 4).

Fig 4: Isokinetic dynamometry device (BiodeX System 4 Pro, BiodeX Medical Systems, Inc., Shirley, NY, USA) (adopted from Sinacore et al. 2017).

b. leg press machine (FL1801 Isolateral Leg Press):

Fig 5: Leg press machine (FL1801 Isolateral Leg Press, BodyKore Inc., Garden Grove, CA, USA) (adopted from BodyKore Inc., 2025).

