2. The participant's feet will be positioned shoulder-width apart on the footplate, with the toes slightly externally rotated and the heels in full contact with the platform.
3. The participant will maintain full contact with the backrest throughout the exercise, with the head and spine supported. The side handles will be grasped to enhance postural stability and balance.

4. The exercise will commence from a flexed knee position, with particular attention given to maintaining proper knee alignment over the feet, avoiding any medial or lateral deviation.
5. The participant will extend the knees and hips to press the platform upward, taking care to avoid full knee lockout at the end of the movement.
6. The platform will then be returned to the initial position in a controlled manner through knee flexion, maintaining proper form throughout the eccentric phase (figure 8).

[figure not shown]

Fig 8: Leg press exercise adopted from (adapted from Martín et al., 2020).

2) Experimental groups: The participant in each subgroup (A, B, and C) will perform the same leg press exercise protocol applied for group D followed by mini squat exercise program with 5 min of submaximal cycling on an ergometer between 2 treatment programs. A total of 18 sessions will be conducted over a six-week period as follows:

1. **Group A:** participants will receive mini-squat program at 30° in addition to leg press program
2. **Group B:** participants will receive mini squat program at 45° in addition to leg press program
3. **Group C:** participants will receive mini-squat at 60° in addition in addition to leg press program

Mini-squat program:

1. Participants will stand barefoot or wear flat training shoes on a stable surface, placing their feet shoulder-width apart with toes slightly pointed outward.
2. A goniometer will be used during the first session to measure the target knee flexion angle (30° for group A, 45° for group B, and 60° for group C) demonstrated once by the examiner on one leg while the participant stands still. This will be followed by passive guidance into the used angles to help the participant recognize the posture and depth, with instructions to remember the sensation for future sessions; goniometer use will be repeated in later sessions only if corrective feedback is required.

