3. Mini-squat session will last 10 minutes. Squat will be performed in a slow and controlled manner (approximately 2 seconds down and 2 seconds up), with short rests of 15–30 seconds allowed every 1–2 minutes as needed. Approximately six minutes of active squatting will be completed per session, with the remaining time allocated for brief rests and transitions (**adapted from Hartmann et al., 2016**) (figure 9).

Fig 9: Mini squat exercise (adopted from Prentice, 2024).

Statistical analysis

All analyses were carried out using IBM SPSS Statistics version 27 (IBM Corp., Chicago, IL, USA).

- Subject characteristics will be analyzed using ANOVA, while the Chi-squared test will be used to compare the distribution of the affected side among the groups
- The Shapiro-Wilk test assessed the normality of the data, followed by Levene's test to verify the homogeneity of variances across groups.
- A mixed MANOVA will be conducted to evaluate the effects of group on the dependent variable(s).
- Post-hoc multiple comparisons were performed with Bonferroni correction to adjust for Type I error.
- Statistical significance was determined at a threshold of $p < 0.05$.

REFERENCES

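### The plan claims participants are blinded to their group, but the programmes differ openly, and it never says whether the strength tester knows the allocation

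*Combined protocol and SAP*

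**What the plan says.** The only blinding statement is in the protocol, under Randomization, allocation concealment, and blinding: "The participants will be blinded to the assigned intervention group". It is unqualified and names no method. The same section provides sealed envelopes for concealment and says the randomisation is done "by another participant not involved in the data collection".

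The programmes are set out under Participants and Treatment procedures:

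- Control: "Control group D: Fifteen participants will receive leg press exercise program only".
- Groups A, B and C: the same leg press, "followed by mini squat exercise program with 5 min of submaximal cycling on an ergometer between 2 treatment programs". On the schedule: "A total of 18 sessions will be conducted over a six-week period as follows".
- Mini-squat program: "Mini-squat session will last 10 minutes". The target angle is "demonstrated once by the examiner on one leg while the participant stands still". The player is then guided passively into it, "with instructions to remember the sensation for future sessions".

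Under Assessment procedures, quadriceps torque is measured in maximal repetitions with encouragement, and the hamstring test follows the same procedure. The tests are repeated three days after training ends. These passages do not identify the tester or say what that person knows. The Statistical analysis section says nothing on masking.

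**The concern.** Two separate things are wrong or missing.

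First, the plan asserts a property that the design does not have. A player who performs a second exercise at every visit, at an angle he has been asked to memorise, knows what he is receiving. So does a player who performs leg press and nothing else.

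Second, the plan is silent on the person whose masking could be arranged in practice, the tester.

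What is at stake is how far the strength comparison can be trusted. Peak torque here is a voluntary maximum. The dynamometer records torque objectively, and strapping and a familiarisation test limit recording and set-up error. None of this makes effort or encouragement equal across arms. If the sentence stays, the trial could be reported as participant-blinded when it was not, and readers could not tell whether the tester was masked.

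**Working it through.** The plan gives no figure for this point, so the check sets its sections side by side and adds one piece of arithmetic on visibility.

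**1. Can a player be unaware of his own programme?**

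| Component | A, B, C | D | Where stated |
|---|---|---|---|
| Leg press | yes | yes, same protocol | Treatment procedures |
| Extra cycling between programmes | 5 min | none | Treatment procedures, experimental groups |
| Mini-squat session | 10 min | none | Mini-squat program |
| Sham or attention control | not applicable | none described | – |
| Sessions | 18 | 18 | Treatment procedures |

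Extra time per session in A–C: 5 + 10 = 15 min.

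Over the trial: 18 × 15 = 270 min (4.5 h), made up of 18 × 5 = 90 min of cycling and 18 × 10 = 180 min of mini-squat session.

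This shows that A–C and D are plainly distinguishable. It is not an estimate of bias.

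**2. Where does the visible difference fall?** A, B and C share one format and differ only in angle. The openly visible difference is therefore A–C against D. All three hypotheses name the comparison with leg press alone. The three stated purposes also compare the angles with one another. There, unawareness of the other angles is conceivable, although each player still knows his own.

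**3. Is the tester masked?** Three provisions might be thought to cover this.

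- *Randomiser kept apart from data collection.* This concerns generation of the sequence. It does not say what the tester knows.
- *Sealed envelopes.* These protect assignment before allocation. They do nothing for a test after six weeks of training.
- *The examiner in the mini-squat section.* This person demonstrates the group's angle and so knows the allocation. The documents do not say whether this is also the tester, so neither masking nor its absence can be inferred.

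The tester's status is therefore unstated.

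**4. Could knowledge of the arm affect the outcomes?** Quadriceps and hamstring torque both depend on effort, and encouragement is required but not scripted. For the ratio, suppose knowledge of the arm multiplies hamstring torque by (1 + a) and quadriceps torque by (1 + b). Then

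observed H:Q = true H:Q × (1 + a) / (1 + b).

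If a = b the effect cancels; if a and b differ it does not. The two absolute strength outcomes are directly exposed. H:Q is exposed only when the effect differs between the muscles. The documents give no values for a or b, so no size follows.

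**The case against.** The strongest reply is that the sentence speaks of the assigned group, not the programme. Players might not know which arm is the control, what the other angles are, or what is hypothesised. What they are told would be in the consent form (Appendix I), which is not in the text available for review, so its content cannot be held against the plan. This stands as a possible meaning, but the protocol does not express it. The correction should use that wording only if it is true and agrees with the consent form.

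Other points have some force:

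- The angle comparisons among A, B and C are less exposed than the comparison with D, and the stated purposes concern those angles. That limits the reach of the problem. It does not remove it from the hypotheses.
- Effort that rises in equal proportion for both muscles cancels in H:Q. This is correct, and the consequence is strongest for the two torque outcomes.
- H:Q is an inclusion criterion, so some testing should precede randomisation. The order of pretest and allocation is not stated. If the pretest comes first, masking matters mainly at the post-test.
- The plan already calls for encouragement without distinguishing arms. A script is therefore a safeguard, not the correction of an error.
- All players come from two clubs and attend one clinic, but no section says that the arms train together. Comparing of programmes is possible and not shown.

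**Conclusion.** The concern holds on both parts. As described, participants cannot be blinded to their own programme, so the blinding sentence is wrong as written. Whether the strength tester is masked is not stated anywhere in the text available.

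The only figure that can be derived is the 15-minute difference per session, 270 minutes in total, and it measures how visible the arms are. The size and direction of any bias cannot be obtained from the documents.

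The conclusion assumes that no sham procedure exists beyond what is described. It does not depend on the content of the consent form or on the examiner being the tester. The design remains usable. The blinding description should be corrected before the trial is reported.

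**What to change.** 1. Replace the blinding sentence with: *Participants are not blinded to their own programme.* Add *They are not told the hypothesis or the content of the other arms* only if that is true and agrees with the consent form.
2. Add: *Pre- and post-test dynamometry is run by an existing staff member who is not told the allocation and does not supervise training.* If staffing does not allow this, write instead: *The outcome assessor is not blinded.* This second form discloses the problem without reducing it.
3. Use one scripted form of encouragement for all players, both muscles and both visits.

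The cost is protocol wording and a short script, with no added participants, visits or equipment. The documents give no staffing information, so splitting tester and trainer depends on the people available. The downside is that the trial can no longer be described as participant-blinded.

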However, research indicates that the contribution of hamstrings during the leg press varies depending on technique and joint positioning. For example, performing the leg press with greater hip flexion angles or deeper ranges of motion increases posterior chain recruitment, allowing the hamstrings and gluteal muscles to contribute more effectively. Additionally, tempo variations, unilateral leg press, and eccentric-focused training have been suggested to enhance co-activation of the hamstrings, thereby helping maintain a healthier H:Q ratio (Jaric, 2002).

To optimize muscle balance, leg press training should not be performed in isolation but rather integrated with targeted hamstring-dominant exercises such as Nordic hamstring curls, Romanian deadlifts, or stability ball leg curls. Combining these exercises ensures proportional development between the knee extensors and flexors, preserving an optimal H:Q ratio and reducing the likelihood of muscular imbalances and knee-related pathologies (Alonso-Cortés et al., 2022; Aagaard et al., 1998).

12-Assessment of muscle strength, H:Q ratio, and ROM:

- Assessment of muscles strength:**

Manual Muscle Testing (MMT) represents the most basic method for evaluating quadriceps and hamstring strength, relying on the examiner's subjective judgment of resistance to applied force. Although widely

implemented in clinical settings due to its simplicity and cost-effectiveness, MMT demonstrates limited validity and reliability, particularly for detecting subtle strength deficits or in individuals with high levels of muscular strength (**Cuthbert & Goodheart, 2007**).

Handheld dynamometry (HHD) provides a more objective alternative by quantifying force output of the knee extensors and flexors. Reported reliability values for HHD are generally strong, with intraclass correlation coefficients (ICCs) ranging from 0.76 to 0.96 for both quadriceps and hamstrings (**Thorborg et al., 2013**). Nonetheless, outcomes are influenced by examiner strength, stabilization strategies, and patient positioning, which reduce its consistency compared with isokinetic assessment, particularly in athletic populations (**Mentiplay et al., 2015**).

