c. Goniometer (Jamar Plus+ Digital 8):

Digital goniometers provide more precise joint range of motion (ROM) measurements than traditional goniometers by offering direct electronic readouts, reducing examiner error. They have demonstrated excellent reliability and validity, with intra-rater ICC values up to 0.96 for knee flexion and 0.92 for extension, and inter-rater ICCs ranging from 0.88 to 0.94. These results highlight their accuracy and reproducibility, making them particularly useful in research and advanced clinical practice (Kolber & Hanney, 2012) (figure 6).

Fig 6: Goniometer (Jamar Plus+ Digital 8" Goniometer, China) (adopted from Jeon et al., 2024).

Assessment procedures:

Participants will be interviewed, and they will be checked for eligibility according to pre-mentioned inclusion criteria. Participants who will be eligible for the study will sign a written consent form, and demographic data regarding height, weight, and BMI will be calculated and recorded. The pretest will be performed 3 days after a familiarization test, which included the same tests in the same order. The same tests will be carried out again 3 days after the last training session.

The assessment procedure will include the following:

1-Measurement of quadriceps strength:

- The participant will be seated on the isokinetic dynamometer chair, with proper posture and alignment ensured.
- The chest, pelvis, thigh, and ankle will be stabilized using adjustable straps to minimize compensatory movements.
- The lateral femoral epicondyle (the anatomical axis of the knee joint) will be aligned with the mechanical axis of the dynamometer arm.
- The lever arm of the dynamometer will be securely attached to the participant's lower leg, just above the ankle, using a padded cuff.

- Test Parameter Settings will be:
 - Mode: Concentric contraction.
 - Velocity: Commonly set at 60°/s for maximal strength.
 - The range of motion (ROM): between 90°knee flexion to full knee extension.
 - Repetitions: 3–5 maximal repetitions.
- The participant will be allowed to perform a submaximal warm-up trial to become familiar with the movement and resistance.
- The participant will be instructed to perform maximal knee extension against the resistance of the device, moving from a flexed to an extended position.
- The test will be conducted unilaterally, assessing one leg at a time.
- The participant will be encouraged to exert maximal effort during each repetition.

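### All players come from two clubs, yet club is used in neither the randomisation nor the model: a modest, cheaply avoided loss of precision and interpretability, not a bias

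*Combined protocol and SAP*

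**What the plan says.** - **Source of players** (Participants): "Sixty male football players from Al-Ahli and Al-Ittihad football clubs in the Kingdom of Saudi Arabia". The number per club is not given. Inclusion criterion 3 requires "Currently training or playing with a registered football club/team".
- **Randomisation** (Randomization, allocation concealment, and blinding): "The enrolled participants will be randomized in a simple randomization way". No strata, blocks or minimisation are described. The Participants section nevertheless states: "Participants will be randomized into 4 equal groups", with 15 in each.
- **Main analysis** (Statistical analysis): "A mixed MANOVA will be conducted to evaluate the effects of group on the dependent variable(s". Club is not named as a factor or covariate, and the text does not say whether the group main effect or the group-by-time term answers the hypotheses.
- **Baseline comparison** (same section): "Subject characteristics will be analyzed using ANOVA, while the Chi-squared test will be used to compare the distribution of the affected side among the groups". Club is not listed.
- **Timing** (Assessment procedures): strength is tested before training, and "The same tests will be carried out again 3 days after the last training session".
- **Outside training**: exclusion criterion 4 bars competitive sport or high-intensity training apart from the trial's own programme, although inclusion criterion 3 requires current club training or playing.

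**The concern.** Club is known before enrolment, has two levels and costs nothing to record. It could matter on the protocol's own reasoning. Chapter II, section 11, says that "leg press training should not be performed in isolation but rather integrated with targeted hamstring-dominant exercises", so hamstring work done elsewhere can affect the H:Q ratio. It is a reasonable inference, though not a statement in the documents, that team-mates share more of such work with each other than with players of the other club.

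If the clubs do differ in how strength or H:Q changes over six weeks, two things follow. The club variance stays in the error term and widens every interval. And if one arm happens to be heavy in one club, a reader cannot tell how much of that arm's result reflects its club mix, because the plan neither reports nor adjusts for club.

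**Working it through.** **Plan's own figure.** The Sample size section gives 48 players for 80% power at alpha 0.05 with four groups, raised to 60. Using a repeated-measures between-factor F test with f = 0.2877, m = 3 measurements and correlation 0 (m, the correlation, and reading 0.2877 as f rather than f² are assumptions):

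- f² = 0.2877² = 0.0828, so 3 × 0.0828 = 0.2483 and V = 0.2483/1.2483 = 0.1989, the printed Pillai value.
- λ = 0.0828 × 48 × 3 = 11.92 on 3 and 44 df gives power 0.800. The stated 48 is reproduced.

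**Cost of a club term if club has no effect.** Error df fall by one, from 44 to 43 at N = 48 (power 0.8000 to 0.7991) and from 56 to 55 at N = 60 (0.8935 to 0.8931).

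**How often the arms are unbalanced.** Inputs: 60 players and arms of 15 (plan); a 30/30 club split (assumption). The SD of the difference in club count between two arms is √(2 × 15 × 0.25 × 60/59) = 2.76 players, or 2.76/15 = 0.184 as a proportion. Random permutation of 60 players into four arms of 15 gives:

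| Assumed split | Given pair differs by ≥5 | Largest gap among four arms ≥5 |
|---|---|---|
| 30/30 | 0.10 | 0.36 |
| 40/20 | 0.085 | 0.30 |
| 45/15 | 0.058 | 0.23 |

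A normal approximation agrees for the 30/30 pair: 4.5/2.76 = 1.63, two-sided probability about 0.10.

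**What an imbalance does.** A 5-player difference is 5/15 = 0.333 of an arm, so the shift is 0.333 × gap. With within-club SD 1, the SE of an arm difference is √(2/15) = 0.365. The average added variance, relative to 2/15 = 0.133, is (gap × 0.184)²/0.133.

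| Assumed club gap (SD) | Shift from a 5-player imbalance (SD) | Shift ÷ SE | Average added variance | SE rises by |
|---|---|---|---|---|
| 0.3 | 0.10 | 0.27 | 2% | 1% |
| 0.5 | 0.17 | 0.46 | 6% | 3% |
| 0.8 | 0.27 | 0.73 | 16% | 8% |

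**Does it damage validity?** One-way ANOVA on change was simulated without stratification (6,000 runs per setting; club gaps 0 to 1.0 SD; splits 30/30 and 45/15). The unadjusted type I error was 0.048 to 0.053 and the mean arm difference was unbiased throughout. Power for a 1 SD effect in one arm, 30/30 split:

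| Club gap in change (SD) | Without club term | With club term |
|---|---|---|
| 0 | 0.783 | 0.775 |
| 0.2 | 0.780 | 0.773 |
| 0.5 | 0.758 | 0.777 |
| 1.0 | 0.679 | 0.776 |

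The small loss at gaps of 0 and 0.2 SD exceeds the one-df cost because, without stratification, club and arm are not orthogonal. Stratifying largely removes that part.

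**Promised equal arms.** Simple randomisation of 60 players gives exactly 15 in all four arms with probability 60!/(15!⁴ × 4⁶⁰), about 0.002. The permutation figures above therefore take the plan's 15 per arm as given, although its stated method would rarely produce it.

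**The case against.** The strongest case is that leaving out a two-level recruitment source is a permissible choice. It has four parts.

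1. *Chance imbalance is not bias.* This stands. A reader might infer that club imbalance contaminates the comparisons or makes the tests anticonservative. The simulation shows otherwise: the error rate holds at its nominal level, because the club variance is already in the standard error.
2. *A stable club difference cancels in a pre/post design.* This stands for the group-by-time term, where only a club difference in change carries through. It does not hold for the group main effect, which averages over time and carries any difference in level. The Statistical analysis section leaves open which is tested, and the sample size is reproduced above with a between-factor test.
3. *The 36% figure exaggerates.* It is the largest gap among four arms, the worst of six pairs. The figure for any one planned contrast is about 10%. Bonferroni comparisons may cover all pairs, so 36% has some relevance, but it should not be read as the risk to a particular contrast.
4. *No club effect is documented, and outside training is limited.* No club split, club difference or club-specific response appears anywhere, and all participants share one clinic and narrow entry criteria. Exclusion criterion 4 on its face limits club conditioning. But it leaves lighter club work untouched and conflicts with inclusion criterion 3, so it cannot be relied on to remove a club effect.

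**Conclusion.** The point holds as a missed, inexpensive improvement. Two clubs, unstratified simple randomisation and a model without club are all plain in the text. The consequence is lower precision and a harder reading of any one result. The documents do not support a claim of bias or of inflated type I error.

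The size is modest unless the clubs respond quite differently: the SE of an arm difference rises by about 1%, 3% or 8% for club gaps of 0.3, 0.5 or 0.8 SD. In about one allocation in ten, a given contrast carries an imbalance of at least 5 players; at exactly 5, the shift is 0.10, 0.17 or 0.27 SD against an SE of 0.37. These figures rest on an assumed 30/30 split and on assumed gaps in change, or in level if the group main effect is tested.

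**What to change.** - **Allocation.** Replace simple randomisation with a concealed list stratified by club, in permuted blocks whose sizes are not disclosed to recruiters. Set the list or club quotas so that each arm totals 15. Blocks alone do not ensure this when a club's number is not a multiple of 4. Club quotas of 28 and 32 work (7 + 8 = 15 per arm). With 30 and 30, the last incomplete block in one club can cover two arms and that in the other club the other two (7 + 8 or 8 + 7). This also resolves the conflict between simple randomisation and four equal groups.
- **Analysis.** Add club as a fixed factor to every outcome model, state that group-by-time is the tested term, and tabulate club by arm.
- **Eligibility text.** Inclusion criterion 3 and exclusion criterion 4 must be reconciled, so that it is clear what club training may continue during the six weeks.

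The cost is a second envelope series and one error degree of freedom (power at N = 48 about 0.800 to 0.799 if club has no effect), with no extra players or visits. If allocation has already taken place, the club term and the club-by-arm table can still be added, ideally before outcome data are examined.

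### Exclusion items 6 and 7 bar healthy players as written, and exclusion item 4 could remove randomised players while no analysis set is defined

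*Combined protocol and SAP*

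**What the plan says.** The lead-in to the Exclusion criteria reads "Participants having any of the following criteria will be excluded from the study". Seven numbered items follow. Five bear on this point by barring something unwanted or by touching on health status:

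- Item 1: "History of acute or chronic injury to the knee, hip, or ankle joint"
- Item 3: "Diagnosed with neurological or systemic disorders affecting muscle function or balance"
- Item 5: "Presence of any contraindication to exercise, such as uncontrolled hypertension or heart conditions"
- Item 6: "Clinically free from lower limb injuries"
- Item 7: "Having no history of neurological, cardiovascular, or musculoskeletal disorders"

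Item 4 of the same list is "Participation in competitive sports or high-intensity training outside the study protocol during the study period". Inclusion item 3 requires players who are active with a registered club at present, and the Participants section draws all sixty from two named clubs. The Delimitation section sets 18 sessions over six weeks.

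The Assessment procedures section says of participants that "they will be checked for eligibility according to pre-mentioned inclusion criteria". It does not mention the exclusion list.

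The Statistical analysis section gives the software, the tests, a Bonferroni correction and a significance threshold. It does not say which randomised players are analysed, or what happens to the data of a player removed after randomisation.

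**The concern.** There are two separate problems.

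**Direction of items 6 and 7.** Both describe good health, yet both stand in a list where meeting any one item keeps a player out. Followed as written, the rule turns away the players the trial wants. Correcting the direction alone leaves a further question. The two items do not have the same scope as items 1, 3 and 5, so screeners would still lack a single rule on injury and a single rule on disorders.

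**Working of item 4.** Whether a player takes part in outside sport during the study can be known only once he is in it. The stated consequence is exclusion. If that means removal, players are lost after randomisation for a reason plausibly related to training load, and so to strength, which is the outcome. Without a stated analysis set, nothing in the plan protects the randomised comparison.

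**Working it through.** The check is mainly a reading of the sections side by side.

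**1. Apply the exclusion list literally to a healthy player** (no injury, no relevant history, no contraindication).

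| Item | Does he meet it? | Consequence |
|---|---|---|
| 1, joint injury history | No | Stays in |
| 3, neurological or systemic disorder | No | Stays in |
| 5, contraindication | No | Stays in |
| 6, free of lower limb injury | Yes | Excluded |
| 7, no disorder history | Yes | Excluded |

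So 2 of the 7 items are inverted, and either one alone bars him. The literal eligible set is not strictly empty. A player with a present lower limb injury away from the three joints in item 1, plus a past musculoskeletal disorder that triggers neither item 3 nor item 5, could pass. That is plainly not the target population.

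**2. Compare scope once the direction is corrected.**

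- Injury: item 1 concerns history and three joints. Item 6 concerns present status and the whole lower limb.
- Disorders: item 7 covers any neurological, cardiovascular or musculoskeletal history. Item 3 is limited to disorders with a stated functional effect, and item 5 to contraindications to exercise.

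Example: a player with a fully recovered thigh-muscle strain passes items 1 and 6, but may fail item 7 if the strain counts as a musculoskeletal disorder.

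**3. Look at the time frames.** Inclusion items 5 and 6 and exclusion item 2 each set a window that ends before the study starts. Exclusion item 4 alone refers to the study itself, which includes at least the six training weeks. Inclusion item 3 refers to the present, that is, to entry. A player in light or off-season club training can satisfy both, so the two are logically compatible. The documents give no season timing and no rule on club training.

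**4. Ask what removal could do to the comparison.** In a group of n randomised players, let k be removed. Let R be the mean outcome (level or change) of those removed and K that of those kept.

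mean of all = [kR + (n − k)K]/n, so K − mean of all = −(k/n)(R − K)

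The bias in a comparison of two groups is the difference between two such shifts. It is zero if the shifts are equal. The documents give neither k nor R − K for any group, so the bias cannot be given a size. If the result is read through change from pre-test to post-test, stable differences in strength between removed and kept players also largely cancel.

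**5. Effect on numbers.** The Sample size section gives a minimum of 48 (12 per group) and a total of 60 (15 per group). The allowance is 60 − 48 = 12 players, or 15 − 12 = 3 per group. Removals under item 4 would draw on that same allowance, and the documents give no expected rate.

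**The case against.** The strongest reply is that part one is a slip that would mislead nobody. Items 1, 3 and 5 show the intended direction, items 6 and 7 are phrased much like inclusion items 5 and 6, and no screener would turn away every healthy athlete. That is right about intent and limits the practical harm. It does not make the written rule correct, and it does not settle the scope differences. One can answer that overlapping criteria all apply and the strictest governs. That is workable, but the plan does not say so.

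On item 4, inclusion item 3 applies at entry and item 4 afterwards, so there is no contradiction. This stands. A commitment at entry, or an off-season study, would satisfy both. The missing analysis set is also a general gap, not one created by item 4. That is true as well, but item 4 is a written route by which players could be removed after randomisation.

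A reader might infer three stronger things, none of which the documents support:

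- *That none of the exclusion items is checked*, because the Assessment procedures section cites only the inclusion criteria. That sentence does not say it replaces the exclusion list, which still states that such players will be excluded. It is loose wording.
- *That removal must differ between groups*, because the mini-squat groups have longer sessions. Item 4 concerns activity outside the protocol, and nothing links session length to club activity.
- *That the comparison is biased by a stated amount.* Any figure would rest on assumed removal rates and assumed differences between players.

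The screening hamstring-to-quadriceps ratio might also look undefined. The device and formula are given, and a familiarisation test uses the same measurements. Only the source and timing of the value used for eligibility are missing.

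**Conclusion.** The point holds in two parts. First, exclusion items 6 and 7 (2 of 7) are inverted as written and contradict items 1, 3 and 5. This is certain from the text. The conclusion that they are misplaced inclusion conditions is an inference, but a strong one.

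Second, item 4, read literally, allows removal after randomisation, and the plan names no analysis set. The absence is certain. Whether the investigators intend removal is not stated. The tension with inclusion item 3 depends on season timing and club duties that the documents do not give. Bias would arise only to the extent that removal differs between groups in number or in kind of player. It is a possibility to guard against, not a demonstrated effect.

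The plan should be amended on both parts. The first makes an operative rule wrong, and the second leaves the randomised comparison unprotected at a place where protection is cheap.

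**What to change.** 1. Move items 6 and 7 to the Inclusion criteria.
2. Reconcile their scope with exclusion items 1, 3 and 5, so that there is one injury rule (site and time) and one disorder rule. Which scope is intended is for the investigators to state.
3. In Assessment procedures, say that eligibility is checked against both the inclusion and the exclusion criteria, and add the source and timing of the screening hamstring-to-quadriceps ratio.
4. Reconcile exclusion item 4 with inclusion item 3, and state item 4 as a commitment made at enrolment.
5. In Statistical analysis, add that all randomised players with outcome data are analysed in their assigned group, whatever their outside activity.

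The cost is text amendment only. Keeping players who take part in club activity may make the outcomes somewhat more variable, and so cost some precision. The documents give no basis for sizing that loss. If the wider wording of item 7 is retained, the pool of eligible players shrinks. Step 5 does not deal with players who have no post-test, for whom a missing-data rule would still be needed.
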